**Single-center, Retrospective Study
of Retro - Auricular Single - Site
Endoscopic, Transoral Endoscopic
Thyroidectomy Vestibular Approach
and Transareola Endoscopic
Thyroidectomy in Patients With
Early Stage Papillary Thyroid
Carcinoma**

Study Protocol

Version date: February 11, 2023

Official Title	Single-center, Retrospective Study of Retro - Auricular Single - Site Endoscopic, Transoral Endoscopic Thyroidectomy Vestibular Approach and Transareola Endoscopic Thyroidectomy in Patients With Early Stage Papillary Thyroid Carcinoma
Brief Summary	The goal of this retrospective study is to compare the safety and efficiency of endoscopic thyroidectomy via retro - auricular single - site approach, transoral endoscopic thyroidectomy vestibular approach and transareola approach.
Conditions	Age: 18 ~ 70 years. Patients with early stage papillary thyroid carcinoma.
Sample Size	160
Inclusion Criteria	
 ● Age 18-70 years old, no gender restrictions. ● Fine-needle aspiration cytology(FNA) confirmed papillary thyroid carcinoma(PTC). ● Early stage PTC (stage T1N0M0). ● Preoperative ultrasonography showed unilateral glandular lobe malignant tumor and the largest diameter was not more than 2cm, without cervical lymph node metastasis and extensive metastasis. ● Patients undergoing thyroid lobectomy and central lymph node dissection. ● Patients who have signed an approved Informed Consent.
Exclusion Criteria	
 ● Patients who do not accept case data collection for various reasons. ● The clinical data unfit this study (at the discretion of the investigator) . ● Patients who have undergone neck surgery or radiotherapy before this trail. ● Patients who have uncontrolled hyperthyroidism.
Elimination Criteria	
 ● Patients who violated the requirements of the research protocol. ● The quality of data records is incomplete and inaccurate. ● Lost cases.
Study Completion	2023-02-28
Locations	1
Statistical Analysis Plan	All analyses were performed using SPSS 26.0, and a P value less than 0.05 was considered significant. Normally distributed quantitative data are represented by mean (SD) [range]. Non-normally distributed quantitative data are represented by M (Q_R) . Comparison between groups was performed using the Mann-Whitney U test. Categorical data are expressed as frequencies and percentages. Comparisons between groups were performed using the χ^2 test or Fisher's exact test.

Study Protocol

1. Background

Thyroid cancer is one of the most common malignant tumors in the head and neck. Among it, papillary thyroid carcinoma accounts for about 70% of thyroid cancer. The degree of malignancy is low, but there is a tendency for multicentricity, and cervical lymph node metastasis occurs early. Due to the development of diagnosis technology, the amount of papillary microcarcinoma is getting higher and higher. At the same time, the change of aesthetic makes young women pursue a scarless neck^{1, 2}. Surgery is the first choice of treatments for early-stage thyroid cancer.^{3, 4} Traditional open surgery tended to leave a long scar on the neck, which affects the cosmetic outcome. At present, many reported approaches, such as trans-areola approach⁵, trans-axillary approach⁶, trans-oral approach^{7, 8} or some combined approaches⁹, all have wider flap dissection or greater body trauma, and at the same time, these above approaches are difficult to achieve complete dissection of central lymph nodes¹⁰. Therefore, based on the experience of transauricular hairline endoscopic thyroidectomy¹¹⁻¹³, we established a new operative method-the Retro-auricular single-site endoscopic thyroidectomy (RASSET). The incision is only 3cm and located at the posterior sulcus of the auricle, which can meet the cosmetic needs. Compared with other endoscopic approaches, the dissection area is small and the flap dissection is small, which may reduce the surgical trauma. The RASSET is easy to resect the upper pole of the thyroid gland, and can achieve complete dissection of the central lymph nodes. The article titled "A comparative study between retro - auricular single - site endoscopic thyroidectomy and transoral endoscopic thyroidectomy vestibular approach: a single - center retrospective analysis" has been published in "Chin J Surg"¹⁴. Guangdong Medical Information Research Institute recognized that there was no report of endoscopic thyroid surgery for this approach at home and abroad, and it also passed the new technology evaluation in the Sun Yat-sen University Cancer Center, and was recognized as an international leader.

Figure 1. A:Sun Yat-sen University Cancer Center Certificates(international innovation). **B:**Guangdong Medical Information Research Institute Certificates(no report of this approach). **C:**Zhonghua Wai Ke Za Zhi(a new approach).

2. Study purpose

2.1 Primary purpose:

Compare the traumatic differences between the three groups by comparing the preoperative and postoperative CRP levels of the three groups.

2.2 Secondary purpose:

Compare the degree of surgical trauma between the three groups by comparing the level of SAA, blood loss, VAS pain score, and postoperative drainage.

Compare the clinicopathologic characteristics between the three groups by comparing the number of resected lymph nodes, and the positive rate of lymph nodes.

Compare the safety between the three groups by comparing the types and rate of complications.

2.3 Primary Outcome Measure:

CRP level

2.4 Secondary Outcome Measures:

- Cosmetic outcome: postoperative cosmetic outcomes
- Surgical outcomes: SAA level, blood loss, VAS pain score, postoperative drainage volume, Operative time.
- Clinicopathologic characteristics: tumor size, number of lymph nodes, the positive rate of lymph nodes.
- Complication: complication rates and types.

3. Study Eligibility

3.1 Inclusion Criteria:

- Age 18-70 years old, no gender restrictions;
- Patient must be suitable candidates for surgery;
- Be able to understand the purpose of the test;
- Preoperative ultrasound showed unilateral glandular lobe malignant tumor and the largest diameter was not more than 2cm, and preoperative imaging examination showed that the largest diameter of central lymph node was not more than 2cm without lateral cervical lymph node metastasis and extensive metastasis;
- Patients who have cosmetic requirements;
- Patients who have signed an approved Informed Consent

3.2 Exclusion Criteria:

- Patients who do not accept case data collection for various reasons.
- The clinical data unfit this study (at the discretion of the investigator) .
- Patients who have undergone neck surgery or radiotherapy before this trail.
- Patients who have uncontrolled hyperthyroidism.

3.3 Withdrawal criteria:

(A withdrawal case refers to a patient who withdraws from treatment for various reasons in study. Patients with the following conditions will be withdrawn from investigational treatment.)

- The patient himself or his legal representative requests to withdraw;
- In the opinion of the investigator, the patient's continued participation in the study will

be detrimental to his health.

3.4 Elimination Criteria:

- Patients who violated the requirements of the research protocol;
- The quality of data records is incomplete and inaccurate.
- Lost cases.

4. Case Screening

4.1 examination items

All cases must complete the following examination items before being considered for entry into this study. It is generally required to be completed within 7 days before treatment.

- Complete medical history and comprehensive physical examination, including symptoms, signs and specialist examination.
- Check items that must be done before routine treatment, including:

Blood routine: neutrophil/lymphocyte ratio,

Coagulation function: d-dimer,

Serological tests: CRP, SAA, procalcitonin, calcium level,

Thyroid function: TSH level, parathyroid hormone level,

Thyroid ultrasonography and FNA, thyroid Computed tomography scan if necessary,

Chest X-ray, abdominal ultrasonography, electrocardiogram.

The above examinations are all routine preoperative examinations, which do not cause additional financial burden on patients.

[figure not shown]

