7.1 Baseline Characteristics of Patients

Gender, Age, BMI, Tumor size, Pathological type, Tumor location, ASA grade.

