7.2 Postoperative Outcomes

- Surgical outcomes: CRP level, SAA level, Drainage volume, intraoperative blood loss, VAS pain score, Operative time.
- Clinicopathologic characteristics: tumor size, number of lymph nodes, the positive rate of lymph nodes.
- Complications: complication rates and types.

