7.3 Primary Outcome Measure: CRP level

8. Code of Ethics

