10.3 Storage of data

The researcher should keep the data intact. According to the principle of GCP in China, for the investigators or hospitals, the data storage should be more than 5 years.

11. Statistical analysis

Professional statisticians undertake statistical analysis tasks and participate in the whole process from experimental design, implementation to analysis and summary. After the study protocol and case report form are completed, a statistical analysis plan shall be formulated. After some necessary modifications shall be made during the study process as required, and a statistical analysis report shall be provided after the data analysis is completed.

All analyses were performed using SPSS 26.0, and a P value less than 0.05 was considered significant. Normally distributed quantitative data are represented by mean (SD) [range]. Non-normally distributed quantitative data are represented by M (QR) . Comparison between groups was performed using the Mann-Whitney U test. Categorical data are expressed as frequencies and percentages. Comparisons between groups were performed using the χ^2 test or Fisher's exact test.

References:

2. Choi JY, Lee KE, Chung KW, et al. Endoscopic thyroidectomy via bilateral axillo-breast

- approach (BABA): review of 512 cases in a single institute. *Surg Endosc.* 2012;26(4):948-955.
 5. Sephton BM. Extracervical Approaches to Thyroid Surgery: Evolution and Review. *Minim Invasive Surg.* 2019;2019:5961690.

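### Preoperative CRP is collected and named in the primary purpose but has no role in the analysis; an unadjusted test of postoperative CRP could be biased if the groups start at different levels

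*Combined protocol and SAP*

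**What the plan says.** Section 2.1 sets the primary purpose: "Compare the traumatic differences between the three groups by comparing the preoperative and postoperative CRP levels of the three groups". Section 2.3 and the later heading "7.3 Primary Outcome Measure: CRP level" name the variable without saying whether it is a postoperative value, a change, or two values compared separately. Section 7.2, headed as postoperative outcomes, lists "Surgical outcomes: CRP level, SAA level, Drainage volume, intraoperative blood loss, VAS pain score, Operative time".

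Section 4.1 requires preoperative blood tests: "Serological tests: CRP, SAA, procalcitonin, calcium level". On timing it says "It is generally required to be completed within 7 days before treatment". The baseline list in section 7.1 is "Gender, Age, BMI, Tumor size, Pathological type, Tumor location, ASA grade", which does not include preoperative CRP.

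For quantitative data, section 11 and the Statistical Analysis Plan row of the summary table give the same sentence: "Comparison between groups was performed using the Mann-Whitney U test". Neither names a covariate, a change score, matching or a regression model. Section 11 also says "After the study protocol and case report form are completed, a statistical analysis plan shall be formulated". The summary table describes the study as retrospective, gives a sample size of 160, and shows a version date of 11 February 2023 and completion on 28 February 2023.

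**The concern.** Three analyses fit the text: postoperative CRP alone, change in CRP, or separate comparisons of the preoperative and postoperative levels. The first and third both contain an unadjusted comparison of postoperative CRP between patients who were not randomised to their approach. Nothing in the design balances preoperative CRP across the three groups. If one group starts higher, and patients who start higher also tend to end higher, part of the postoperative difference reflects who received which approach. The plan would read it as surgical trauma. This is the primary outcome, and the value needed to adjust for the gap is already a required test.

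**Working it through.** **Inputs from the documents.** Total 160, three groups, P below 0.05. The 160 cannot be reproduced, because no effect size, SD, power or split is given.

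**Assumptions.** Equal split, 160/3 ≈ 53 per group; two-sided test; log CRP normal with postoperative SD 1; preoperative gap g in SD units between two groups; pre/post correlation ρ of 0.1, 0.3 or 0.6; no true effect of approach. Rates are for one pair of groups.

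**Scenario A: groups would not differ at a given preoperative CRP.** The postoperative-only contrast has bias ρ × g. Its standard error is √(2/53) = 0.194. The approximate false-positive rate is Φ(ρg/0.194 − 1.96) + Φ(−ρg/0.194 − 1.96).

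Worked example, ρ = 0.6 and g = 0.3: bias 0.18; 0.18/0.194 = 0.93; Φ(−1.03) + Φ(−2.89) = 0.151 + 0.002 ≈ 15%.

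Simulated rates for the Mann-Whitney U on postoperative CRP (20,000 runs per setting) agree with the formula to within about 2 percentage points:

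| Gap | ρ = 0.1 | ρ = 0.3 | ρ = 0.6 |
|---|---|---|---|
| 0.2 SD | 5% | 6% | 9% |
| 0.3 SD | 5% | 7% | 15% |
| 0.5 SD | 6% | 11-12% | 31-32% |

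With preoperative CRP as a covariate, the rate in this scenario is about 5%. With no gap, every method stays near 5%.

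**How plausible are the gaps?** By chance alone, a pair differs by at least g with probability 2 × [1 − Φ(g/0.194)]. That is 12% for 0.3 SD and 1% for 0.5 SD. For at least one of the three pairs, simulation gives 27% and about 3%. A 0.5 SD gap would in practice need systematic selection.

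**Scenario B: a stable group difference simply persists after surgery.** Let k be the preoperative SD divided by the postoperative SD, on the log scale. The biases are then:

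- postoperative-only: k × g
- adjusted: (k − ρ) × g
- change score: 0 (against (ρ − k) × g in scenario A)

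The adjusted bias is smaller in size than the postoperative-only bias when ρ/k lies between 0 and 2. At g = 0.5:

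- ρ = 0.1, k = 1: adjusted bias (1 − 0.1) × 0.5 = 0.45, against 0.50 unadjusted; false-positive rates about 60% and 70%.
- ρ = 0.6, k = 0.25 (ratio 2.4): adjustment does worse, 19-20% against 9-10%.

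**Imprecise baseline.** If a single preoperative value had reliability 0.6 (an assumption), scenario A with ρ = 0.6 and g = 0.5 leaves an adjusted bias of 0.6 × 0.5 × (1 − 0.6) = 0.12 SD. The rate is then about 10%, against about 31% unadjusted.

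**The case against.** The postoperative-only reading fits section 2.1 least well, since that sentence names both CRP values. Only the section 7.2 heading supports it, and the same list holds blood loss during surgery and operative time, so the heading is weak evidence of timing. This stands as a limit: the text is under-specified, not contradictory. It does not remove the concern, because comparing the two levels separately still includes the same postoperative test.

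Under that reading, descriptive summaries would display a preoperative gap whatever its P value. That also stands. But displaying a gap does not adjust for it, and a preoperative Mann-Whitney test would miss a 0.3 SD gap in about 68% of runs, so a non-significant result would give little reassurance.

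A further plan is promised in section 11, and the flowchart in section 5 is not visible here. Either could settle the variable or the draw. The point is therefore confined to the visible text, including the summary row that carries the plan's own title.

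Finally, adjustment is no cure, as scenario B and the imprecise-baseline case show. That stands in full. It is a reason to report the change analysis beside the model, not to keep an unadjusted test alone.

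**Conclusion.** The point holds as a cheap improvement. The visible plan names preoperative and postoperative CRP for the primary comparison, requires the preoperative value, and then gives it no role beside an unadjusted test. The possible bias depends on two facts that the documents do not supply: a preoperative gap, and an association between the two CRP values. At gaps of 0.2 to 0.3 SD the illustrative inflation in scenario A is nil to modest: 5-9% and 5-15%, against about 5% with adjustment. All of these rates rest on the assumed equal split, normality and correlations.

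Three stronger readings are tempting and unsupported:

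- A reader might infer that the primary comparison is biased, with a false-positive rate near one in three. That needs a 0.5 SD gap and ρ of 0.6, and no section shows such selection.
- A reader might infer that adjusting makes the comparison valid. It is exact only in scenario A with a well-measured baseline.
- A reader might infer that a log-scale model makes rank methods unnecessary. The plan itself provides for non-normal data, and every rate above assumed normal log CRP.

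**What to change.** In section 11, with a cross-reference from 2.3 and 7.3, wording to this effect:

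> The primary variable is log CRP at one named postoperative draw that is available in the records for all three groups. It is analysed in one linear model with approach (three levels) and log preoperative CRP, giving adjusted ratios with 95% confidence intervals. Change in log CRP by approach is reported beside it as a sensitivity analysis. The model assumes that groups would not differ at a given preoperative CRP; the change analysis assumes that a stable group difference would persist unchanged. Adjustment reduces bias from preoperative CRP but may not remove it, since a stable group difference or an imprecise single baseline value can leave some. It does not address other confounding by choice of approach.

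Also state how values below the assay limit are handled. Keep a rank-based check, such as a rank ANCOVA, for clearly non-normal residuals. Add preoperative CRP by group to the section 7.1 table. The primary contrast among the three groups and any multiplicity rule still have to be stated; this change does not supply them.

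The cost is wording, a records check for a common draw, and some reanalysis. Model assumptions need checking, and some preoperative values may be early or missing because the 7-day window is not absolute. Completion falls 17 days after the version date, so if CRP values have already been examined, label the change post hoc.

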4.2 Case screening

According to various examinations, those who meet the inclusion criterias are screened out.

The patients entered the study after completing the required examinations and being evaluated according to the inclusion criterias. Then sign the informed consent form and get treatment.

5. Study Process

Figure 2. flowchart

6. Surgical Technique

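### Sections 3.2 and 3.4 allow discretionary exclusion and whole-patient elimination, with no outcome-blind rule, outcome-by-outcome handling of missing data, or reporting of removals by approach

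*Combined protocol and SAP*

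**What the plan says.** Section 3.2 lists objective exclusions (earlier neck surgery or radiotherapy, uncontrolled hyperthyroidism) and refusal of data collection. Beside them stands an open clause: "The clinical data unfit this study (at the discretion of the investigator". The term unfit is not defined.

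Section 3.4 then eliminates three kinds of case: "Patients who violated the requirements of the research protocol"; those where "The quality of data records is incomplete and inaccurate"; and lost cases. It lists no violations, sets no completeness threshold and gives no follow-up window that would define a lost case. The synopsis repeats both sets of rules.

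The synopsis describes the design: "The goal of this retrospective study is to compare the safety and efficiency" of three approaches. The primary outcome is CRP, before and after surgery (Sections 2.1 and 2.3). Section 2.2 adds: "Compare the safety between the three groups by comparing the types and rate of complications".

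The statistical plan (synopsis row and Section 11) names software, a significance level, summary statistics and tests. It defines no analysis set and no missing-data method. Sections 10.1 and 10.2 provide for monitor review of the case report form, no changes after that, statistician queries and a joint database lock.

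**The concern.** Sections 3.2 and 3.4 are stated rules for taking patients out, and several rest on judgement. In a retrospective study, the person judging whether a record is unfit or too incomplete may be able to see the postoperative CRP and any complication. A complicated course can also plausibly affect how complete a record is, or whether the patient is lost.

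If removal depends on outcome and does so to a different degree in the three groups, the surviving groups no longer represent the patients operated on, and both the primary and the safety comparison are distorted. If removal is similar across groups, the comparison mainly loses precision. Because removals need not be reported by approach, a reader could not tell which case applies.

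Removing a whole patient has a further cost. A patient with a known complication but no usable postoperative CRP could disappear from the complication comparison as well.

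**Working it through.** **1. Could outcomes be known when cases are removed?** The synopsis calls the study retrospective. The document carries "Version date: February 11, 2023" and gives completion as 2023-02-28, which is 28 − 11 = 17 days later. With 160 patients, 160/17 = 9.4 operations per day would be needed, so under this version most operations had probably already taken place. Against this, Section 4.2 states "The patients entered the study after completing the required examinations and being evaluated according to the inclusion criterias" and places consent before treatment; Section 8.1 places it before enrollment. On that sequence a 3.2 exclusion could precede surgery. The 3.4 eliminations (violation, poor record, loss) could still arise after it.

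**2. Does anything visible govern removal?** Sections 10.1 and 10.2 protect what a record says, not which patients remain. Section 11 and the synopsis contain no analysis set, no missing-data rule and no count of removals.

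**3. Which CRP is affected?** Section 4.1 requires CRP among the examinations completed before entry. A missing preoperative CRP is therefore an entry failure. Points about blinding and missing data concern postoperative CRP only.

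**4. Scale for CRP.** The plan gives no group split, SD, effect size or dropout allowance, so every input except the 160 and the 0.05 level is assumed. Inputs: 160/3 ≈ 53 per group; no true difference; each patient has probability f of being a removable case, with CRP shifted up by s SD, the same in both groups; two-sided Mann-Whitney test at 0.05; 10,000 simulated pairs per cell (Monte Carlo standard error about 0.2 points near 5% and 0.35 near 14%).

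| f, s | removed from one group only | half as many removed from the other | equal removal |
|---|---|---|---|
| 10%, 1 SD | 7.6% | 5.7% | 5.1% |
| 10%, 1.5 SD | 9.1% | 6.3% | 5.0% |
| 15%, 1 SD | 9.9% | 6.4% | 5.0% |
| 15%, 1.5 SD | 14.3% | 7.9% | 5.3% |

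A repeat with 6,000 pairs per cell gave 6.7%, 9.0%, 9.8% and 14.6% in the first column and 5.3%–7.6% in the second. The low end is therefore better read as about 7%. In round figures: 7%–14% for one-group removal, 5%–8% for partly balanced removal, 5% for equal removal.

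**5. Scale for complications.** Assume 5/53 = 9.4% in each of two groups and drop k complicated cases from one, giving (5 − k)/(53 − k). Fisher P (two-sided) is against 5/53.

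- k = 1: 4/52 = 7.7%, P = 1.00
- k = 2: 3/51 = 5.9%, P = 0.72
- k = 3: 2/50 = 4.0%, P = 0.44
- k = 4: 1/49 = 2.0%, P = 0.21
- k = 5: 0/48 = 0%, P = 0.058

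No P value falls below 0.05. The distortion is in the reported rates more than in the test.

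**6. What bounds would show.** With 2 complications among 48 patients of known status and 5 unknown, the observed rate is 2/48 = 4.2%. The best case is 2/53 = 3.8% and the worst case (2 + 5)/53 = 13.2%.

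**The case against.** The strongest reply is that this is a possibility and not a demonstrated fault. Bias needs removal that is both outcome-related and unequal between approaches, and no passage points to either. That stands.

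A reader might infer more from the Background statement that "we established a new operative method-the Retro-auricular single-site endoscopic thyroidectomy (RASSET": that the investigators had an interest in one approach and used the clauses to favour it. The documents do not support this. The statement is a reason to make removals checkable, not evidence about how they were made. For the same reason, simulations that delete the highest CRP values from one group overstate the case. Dropping the top 3 to 11 of 53 gives false-positive rates of about 9% to 40%, but that presumes selection directly on the outcome, for which the text gives no ground.

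The missing rules may exist elsewhere. Figure 2 (the flowchart) is not shown and may carry counts, and Section 11 says that a statistical analysis plan will follow once the protocol and case report form are complete. This limits the point to the visible text. Counts in a flowchart would still not make the decisions outcome-blind, and the synopsis row headed as the statistical analysis plan has no such rules.

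The timing is inferred: the version date is not shown to be the start date, and an earlier version with the same rules cannot be ruled out. It is also tempting to read Section 3.4 as certainly removing anyone with a missing postoperative CRP from every analysis. That is one possible reading, which the text does not settle.

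Finally, the choice of analysis set is partly a matter of judgement, and a set without violators can be legitimate if the removals are disclosed.

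**Conclusion.** The point holds as a gap that should be fixed, with medium confidence. The stated rules leave the postoperative CRP and complication comparisons open to selection bias, and the visible text gives no means of preventing or detecting it. The documents do not show that bias occurred, its direction or its size.

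The figures are illustrative and rest on assumed group sizes, removal fractions and CRP shifts. The upper end of the CRP range needs every high-CRP case removed from one group and none from the other; with partly balanced removal the error rate stays close to nominal. For complications, the practical harm would be an understated rate in one group, such as 4.0% in place of 9.4%, more than a false significant result.

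The conflict between the retrospective label and the consent sequence in Sections 4.2 and 8.1 needs its own reconciliation and is not part of this point.

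**What to change.** 1. Replace the discretionary clause in Section 3.2 and the synopsis with listed, objective preoperative reasons. Apply them to all consecutive eligible patients in a stated date window, without view of postoperative CRP or complications. Keep refusal of data collection as an exclusion.
2. Do not eliminate a whole patient for a partial record. Handle missing data outcome by outcome, so that a missing postoperative CRP does not take a patient out of the complication comparison.
3. Present an analysis of all eligible operated patients by the approach started. Show any set that drops violators only as a sensitivity analysis.
4. Report every exclusion, elimination and unknown outcome by approach and reason, with best-case and worst-case bounds for complications.

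The cost is protocol and SAP wording, one table or flowchart, and some extra record extraction. Lost or poor records may yield little, so some outcomes will stay unknown, and complication rates may look slightly less favourable. If case selection is already complete, items 2 to 4 can still be done from the records.
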